Recruitment process: When an eligible candidate is identified per the screening process above, the research team will contact the patient's primary care physician and inform them of this study. If the patient's primary care physician agrees that the patient would benefit from inclusion in this study, they will reach out to the patient and describe the trial to them. If the patient agrees to be contacted by the research team, their care team member will share their information with a member of the research team via secure message and a member of the team will reach out via the participant's preferred method of communication (phone, email, etc). Due to the COVID- 19 pandemic and the fact that diabetes is a risk factor for the virus, all participants will undergo the informed consent process remotely. The research team will make contact with the participant via the mechanism shared with them by the treating team, introduce the project and ask if the participant would like to undergo the informed consent process via an online REDCap survey (screenshots attached) or via a paper consent form sent in the mail. The research team member will then send the Informed Consent Form (ICF) to the participant via either a URL by email or a paper ICF by mail. The research team member will set up a time to discuss the ICF with the participant either by phone or video chat and will describe the study to the participant, review the risks and benefits outlined in the study consent form and address any questions from the participant before asking them for their consent to participate in the study. After consent is obtained, participants will complete an intake survey ("Participant Information Survey") and will be randomized to either the intervention or control group. All participant information obtained during enrollment will be stored securely in a HIPAA-compliant and PHIsafe Stanford Medicine Box folder.

Device setup:

After consent is obtained, the participant's treating physician will communicate their desired insulin protocol with the research team. The information communicated will include the following:

- Starting insulin prescription
- Goal fasting blood sugar
- Titration parameters (e.g. Increase starting dose by 2 units every 3 days if not at goal fasting blood sugar)
- Situations in which they would want their patient to contact their provider or seek immediate medical attention and call 911/report to an ER.

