This information will be communicated with the research team via either a custom Epic order set currently in development or a secure online portal developed by the research team. The provider will only have to provide the patient's unique study ID in order to enter this information in the portal. This ID will be securely emailed to the provider upon enrollment of the patient. The provider will be asked to confirm their prescription inputs via the secure online portal to reduce the probability of erroneous data insertion. The provider will also have to confirm the ID of the patient to prevent the provider from erroneously placing a prescription for the wrong patient. No identifying information will be collected by the portal. For participants in the intervention group, this information will be programmed into the digital voice assistant application. For participants in the control group, this information will be recorded for future data analysis.

Intervention group:

Due to the COVID-19 pandemic and the fact that diabetes is a risk factor for the virus, we will mail devices to participants in the intervention group. We will also provide them with the option to set up a phone call or video chat with a member of the research team to help them with device set up.

Device setup will include the following steps:

- Open Alexa Echo Dot package and plug in to power
- Downloading the "Alexa" smartphone application
- Through the Alexa smartphone application, enabling our custom application (called an "Alexa Skill").
- Logging in to our custom application with a unique study ID that is linked to the participant's insulin protocol.

A detailed document called "Alexa Setup Instructions" will be provided to subjects that go into granular detail on how to set up the device as well as its functionalities (screenshots attached).

The entire set up process should take about 5-10 minutes.

Control groups:

For participants in the standard of care control group, we will email them a copy of a blood sugar and medication administration log for them to fill out electronically through REDCap or print and fill out ("Blood Sugar Log"). If a participant doesn't have access to a printer, we will mail them a copy of the log.

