As an additional control, a subset of patients receiving the voice assistant device will also be given a blood sugar and medication administration log and will be asked to use both the voice assistant and the blood sugar and medication administration log for 2 of the 8 weeks they are participating in the trial ("Blood Sugar Log - 2 weeks only")

Data collection:

Data will be collected daily from participants in the intervention and control groups of the study. Participants in the intervention group will be able to interact with our custom app by speaking with their Echo Dot. Participants will be instructed to "check in" with the app once daily at which point the app will collect information about recently checked blood sugars and recent administration of insulin. Data collected by the device will be read back to the patient for confirmation. At the end of the check in, the app will remind patients about the details of their insulin regimen. Based on the patient's self-reported data, this reminder might include a prompt to change the dose of their insulin. All reminders and prompts will be strictly based on the physician-prescribed insulin protocol at the beginning of the study, and prompts will include a summarization of the rationale behind the recommendation (e.g. "Your fasting blood sugars are still above goal. Based on your prescribed treatment plan, you should increase your dose of Lantus to 17 units."). No automated decisions will be made by the voice assistant. The voice assistant will only be assisting the patient with instructions that patients are normally given in writing by their provider.

An instruction manual will be provided to the patient with details on how to interact with the device ("Alexa Setup Instructions"). The only data collected from the patient will be patient-reported blood sugar data and medication administration occurrences. The audio data collected by the device is encrypted and sent to the Amazon cloud for processing into relevant text. The text data is supplied to our application for analysis and storage. Our application will not receive or store any audio data. No protected health information will be collected by our app. All data will be de-identified and stored in the Amazon Web Services cloud. All data will be linked to a participant's unique study ID. A document linking a participant's unique ID to their name and medical record number will be stored on the secure PHI-safe Stanford Medicine Box server.

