Amazon Echo devices (and all similar voice assistant technologies) record audio during user interactions. This audio data is encrypted and sent to the Amazon cloud for processing into relevant text. The text data is supplied to our application for analysis and storage. Our application will not receive or store any audio data. All audio data collected by Amazon Echo devices are visible in the Alexa app for users to see and delete. Furthermore, Amazon explicitly states that its devices do not record audio data when users are not interacting with its devices. Whenever an Amazon Echo device is recording audio data, a special indicator light will turn on to alert the user. These details will be included in the informed consent process and patients will be instructed on how to delete audio recordings in their Amazon privacy settings if desired.

e. Alternative Procedures or Courses of Treatment

There are no other alternative procedures for collecting data from a digital voice assistant in a patient's home. No standard treatments will be withheld from participants. The alternative is not to participate in the study.

f. Will it be possible to continue the more (most) appropriate therapy for the participant(s) after the conclusion of the study?

Yes.

g. Study Endpoint(s)

We will be evaluating the end points every 2 weeks for 8 weeks. The clinical end points we will be monitoring are blood sugars obtained through standard of care treatment. The study will not be terminated early for any foreseeable reason. The study will end after two months of data collection per patient. During the two months of data collection, the treating physician will be able to make changes to the patient's insulin regimen at any time but logging into our secure research portal. These changes will be reflected instantly in our Alexa application.

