6. PARTICIPANT POPULATION

a. Planned Enrollment

- (i) 50 participants
- (ii) 50 participants
- (iii) Patients at Stanford Internal Medicine Clinics with a diagnosis of Type 2 Diabetes who are clinically indicated to initiate or increase their long acting insulin.

b. Age, Gender, and Ethnic Background

The age range of this study is 18 years of age or older. There are no conditions on the gender or ethnicity of the participant. Male and female participants are going to be enrolled and we aspire to keep an appropriate demographic distribution.

c. Vulnerable Populations

No vulnerable populations will be targeted in this study.

d. Rationale for Exclusion of Certain Populations

Children will not be included in the study because the Internal Medicine team involved specialises in adult care.

e. Stanford Populations

N/A

f. Healthy Volunteers

None

g. Recruitment Details

Our team will recruit patients with type 2 diabetes who have been recently started on insulin (or who are having active adjustments to their insulin regimen). To identify patients that may be eligible for recruitment, our team will use Stanford's STARR cohort discovery tool and an Epic workbench report overseen by [name], the Stanford Population Health Medical Director, and [name], the Stanford Population Health Quality manager. We will use these tools to create a report of patients at Stanford Internal Medicine and Endocrinology clinics with type 2 diabetes and a recent hemoglobin A1c greater than 8%. Specifically, this is done through a cohort discovery of patients who have seen providers who practice at the Stanford primary care and Endocrinology clinic sites. In addition, we will also be identifying patients through advertisements through the Stanford Diabetes Research Core (<https://sdrc.stanford.edu/sdrc-research-cores/detc/home>). Specifically, the recruitment director with the core, [name], will be giving us access to a listserv of Stanford-affiliated patients who have requested to be contacted about diabetes-related clinical trial opportunities.

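### The protocol ties app prompts to the starting insulin plan although portal changes are meant to update the app, and an insulin change not entered in the portal has no described route into the app during the 8 weeks

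*Protocol*

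**What the plan says.** Section 2.a (Data collection) fixes the source of the app's messages: "All reminders and prompts will be strictly based on the physician-prescribed insulin protocol at the beginning of the study". The same text makes those messages a routine part of each daily session: "At the end of the check in, the app will remind patients about the details of their insulin regimen".

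Section 2.g (Study Endpoint(s)) describes what happens when the plan changes: "the treating physician will be able to make changes to the patient's insulin regimen at any time but logging into our secure research portal" (the context shows that this means by logging in). It adds: "These changes will be reflected instantly in our Alexa application".

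The starting plan is supplied under Section 2.a (Device setup), where "the participant's treating physician will communicate their desired insulin protocol with the research team". It is sent "via either a custom Epic order set currently in development or a secure online portal developed by the research team". Entry in the portal needs the participant's study ID, and "This ID will be securely emailed to the provider upon enrollment of the patient".

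More than one prescriber may be involved. Section 6.g recruits from "a report of patients at Stanford Internal Medicine and Endocrinology clinics with type 2 diabetes", and it provides for contact with primary care providers, endocrinologists or both, according to who manages or co-manages the patient's diabetes.

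**The concern.** Taken literally, the two statements about the source of the prompts cannot both hold: one ties them to the plan at study start, the other lets the plan change at any time with immediate effect. The sentence governs the insulin dose that a device reads out to a patient, so it should be exact.

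The wording also draws attention to a practical question. The portal is the only mid-study route into the app that the protocol describes. Insulin can be changed elsewhere: the treating physician may alter the dose at a visit and not open the portal, or a co-managing clinician may alter it independently. The app would then go on presenting the old plan as the doctor's current instruction. What is at stake is the safety of voice-arm participants. No bias in any outcome is claimed, and the SAP's sample size is not affected.

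**Working it through.** The plan gives no figure on this point to reproduce. The check compares the protocol's statements and then gives one illustrative count.

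**Step 1: which rule governs.** Section 2.a (Data collection) refers to the start of the study. Section 2.g describes a working update mechanism in specific terms. Sections 2.b and 7.a refer to the physician's plan with no time limit. Section 2.g is therefore the operating rule, and the phrase in Section 2.a is the one to correct.

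**Step 2: could a change made outside the portal reach the app during the 8 weeks?**
- Participant: under Section 2.a (Data collection) the app takes only blood sugar readings and records of insulin taken. No way to report a new prescription is described.
- Medical record: Section 2.a (Data analysis) has the latest insulin prescription read only for participants who have finished all 8 weeks, when app use is over.
- Epic order set: Section 2.a (Device setup) describes it for the initial plan only.
- Portal: it works if someone makes the entry. No supplied text asks prescribers to enter a change made elsewhere, or to pass it on for entry.
- Monitoring: Section 7.e marks its review items as not applicable and names the Protocol Director as sole monitor. No mid-study reconciliation of prescriptions is described.

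**Step 3: do the safeguards detect a superseded plan?** Readback (Sections 2.b and 7.a) confirms the reported sugar values. The provider's limits on the size and frequency of increases and on the maximum dose (Section 4.a) belong to the plan already loaded. The hypoglycemia protocol (Section 4.a) responds to low sugars. All of these limit harm, but none tells the app that the plan has changed.

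**Step 4: illustration.** Inputs: the example in Section 2.a (Device setup) of 2 units every 3 days while fasting sugar is above goal; a clinician who decided to hold the dose; and an assumed delay of D days before the portal is updated, counted from a step on the day of the change.

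Further upward prompts = floor(D / 3); units = 2 × prompts.
- D = 7: floor(7/3) = 2 prompts; 2 × 2 = 4 units.
- D = 14: floor(14/3) = 4 prompts (days 3, 6, 9, 12); 2 × 4 = 8 units.
- D = 28: floor(28/3) = 9 prompts; 2 × 9 = 18 units.

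The three delays are assumptions. The counts also need fasting sugars to stay above goal and the participant to follow the app, and the maximum dose and the hypoglycemia protocol can cut them short.

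**The case against.** The strongest reply is that the conflict is editorial. The phrase in Section 2.a sits beside a statement that the device makes no automated decisions, and its purpose is to say that prompts come from a prescription. This stands: a reader might infer that the app is frozen at the starting plan, but Section 2.g shows that it is not.

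Second, the portal is the stated route and needs little effort, so it is nearly self-evident that a change not entered there does not arrive. That is fair. The useful point is that nothing supplied prompts anyone to make the entry or tells the participant what to do meanwhile.

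Third, a reader might infer that the problem lies mainly with co-managing providers and that responsibility is otherwise clear. The documents do not support this. They show that co-management is expected, but give neither its frequency nor the rate of changes outside the portal, and they do not say that a co-manager lacks the study ID or portal access. A sole treating physician who skips the portal leaves the same gap.

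Fourth, a written titration plan also goes out of date when a prescriber changes the dose, and the documents do not show how much risk the app adds. This stands as a limit on the size of the concern. The difference is that the app repeats its plan every day, and the sample script in Section 7.a presents the dose as the doctor's instruction.

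Finally, the Alexa setup instructions and the hypoglycemia attachment were not in the supplied text, and consent pages were removed. Any of these may already tell participants what to do when their insulin changes.

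**Conclusion.** The point holds as a minor patient-safety improvement, with medium confidence. Section 2.a is worded inconsistently with Section 2.g and should be corrected to match it. In the supplied text, an insulin change that any prescriber makes without a portal entry does not reach the app during the 8 weeks, so the daily reminder could voice a superseded dose.

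The number of participants affected is unknown. The 4 to 18 units for assumed delays of 7 to 28 days should not be read as a bound or a forecast: they rest on an example titration rule, invented delays, persistently high fasting sugars and a participant who follows the app over the clinician. A reader might also infer a distortion of the trial's results, but the documents give no basis for that.

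**What to change.** 1. In Section 2.a (Data collection), tie prompts to the plan *as currently held in the portal*, so that it agrees with Section 2.g.
2. End the app's regimen reminder with one fixed sentence, for example: *If any clinician has changed your insulin since this plan was set, follow the newer prescription and contact your treating physician's clinic so this plan can be updated.* If the setup instructions already say this, only the spoken sentence is new. It collects no data.
3. In the provider contacts already planned (the study ID email in Section 2.a and the contacts in Section 6.g), ask every managing prescriber, including a sole treating physician, to enter insulin changes in the portal during the 8 weeks or send them for entry. This does not restrict who may prescribe.

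The cost is one phrase, one sentence in the app and one line to providers. The downsides are a slightly longer check-in and a few extra clinic calls, both in the voice arm only. The spoken sentence is also not itself part of the physician's prescription, so Section 2.a should name it as a standing safety message, because that section limits prompts to the prescribed plan.

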1. PURPOSE OF THE STUDY

a. Brief Summary

The purpose of this study is twofold:

- (1) To evaluate the feasibility of a digital voice assistant to help patients manage insulin-dependent diabetes between routine clinic visits. Specifically, the custom app that we will develop will help patients log their blood sugars and medication use, as well as help them adjust their insulin dose based on a protocol that their physician prescribes.
- (2) To evaluate the effects of such an intervention on specific medical outcomes, such as medication adherence, blood sugar control and time to optimal insulin dose, as well as patient self-efficacy measures.

The digital voice assistant used will be an Amazon Echo Dot and it will use a custom application (app) to help patients manage their diabetes at home.

b. Objectives

We hope to learn whether a digital voice assistant can be reliably used by patients at home between clinic visits to improve management of insulin-dependent diabetes. We hope that this improved management will translate into improved medical outcomes. In the future, the findings of this study could serve as a first step towards developing an integrated outpatient solution that leverages voice assistant technology in the patient's home to improve management of multiple chronic medical conditions.

c. Rationale for Research in Humans

The purpose of this study is to test the efficacy of a digital voice assistant in individuals with insulin-dependent diabetes.

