Patients in the control group will use their provided log, labeled with their unique study ID, to record their daily blood glucose checks and insulin adherence. This is part of the standard of care in patients with insulin-dependent diabetes. At the end of the trial period, we will collect this log from patients for data analysis. Participants can choose to securely email or upload this log to the research team through REDCap, or if they prefer, they will be provided with a pre-paid envelope to mail the log free of cost.

Finally, user satisfaction survey data will be collected at the beginning and end of the study from patients in the intervention and control groups. The first survey will include "Problem Areas in Diabetes" ("PAID") questions validated in the literature as a rapid screen for diabetes-related emotional distress (<https://pubmed.ncbi.nlm.nih.gov/19841892/>). This survey is labeled "Diabetes Attitudes (PAID) Survey" (screenshots attached). The second survey will include questions specifically tailored towards interrogating the patient's attitude toward and comfort with insulin dose adjustments ("Medication Adherence Survey"). The third and final survey will include questions on attitudes towards healthcare technology ("Health Technology Survey"). All surveys will be collected online via REDCap.

Data analysis:

Members of the research team will review the collected blood sugar and insulin administration data for analysis. Specifically, we will analyze the collected blood sugar data to determine how often blood sugars were checked and how well-controlled they were. We will also analyze insulin administration data to determine how adherent participants were to their prescribed regimen and how effectively participants were able to titrate their insulin to an effective dose. We will also analyze study survey data to assess participant's diabetes selfefficacy and attitudes towards healthcare technology.

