In addition to reviewing data collected by our app and REDCap, the research team will also access the medical record of participants who have completed the trial to obtain certain lab results and medication data to help supplement any missing data from the trial. Specifically, the research team will obtain recent blood sugar and Hemoglobin A1c values, as well as the most recent insulin prescription. This will help the research team perform data analysis in cases where trial data are incomplete. Please note that this is only for participants who have been consented, enrolled and have completed the full 8 weeks of the trial.

If participants decide to withdraw from the study, they can do so at any time by contacting [name] at [contact] or [contact]. After study completion, participants will be able to keep their Amazon Echo device for personal use. Their specific login ID will be disabled which will preclude them from using our custom application after study completion. If participants decide to withdraw from the study before completion, they will be asked to return their Amazon Echo device. They will be provided with pre-paid packaging to do so.

Infection control strategies implemented to ensure the safety of the research staff/faculty who will come to campus and to mitigate risks to them and their families:

1. Personnel are trained on the need to stay home and get tested if they have a new cough, fever, difficulty breathing, chills, muscle pain, headache, sore throat, recent loss of taste or smell.
2. All research staff/faculty will follow Stanford's social distancing protocol, which includes:
 - a. Maintaining physical distancing.
 - b. Use of face coverings and eye protection.
 - c. Frequent handwashing and use of hand sanitizer.
3. Researchers and support staff returning to campus will be required to use the Health Check tool to report health status each day.
4. There will be no participant-facing research staff as the informed consent and patient enrollment process will be conducted virtually.

Infection control strategies implemented to ensure the safety of the research participants:

1. All devices will be cleaned prior to being mailed to the participant.
2. Participants will perform self-setup of their device to avoid the need for an in-person visit with research staff.

b. Procedure Risks

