7. RISKS

a. Potential Risks

i. Investigational devices

As stated earlier, instructions to patients to change their insulin dose will always strictly adhere to the physician-prescribed insulin protocol. However, if the patient inaccurately self-reports blood glucose data, dose adjustments based on this data can cause medical complications. To minimize the risk of this, the application will ask the patient to confirm

self-reported data, and when the instructed intervention is read back, the device will again summarize the patient's self-reported data and be clear that the intervention is based on the data provided by the patient and is as instructed by the patient's provider (e.g. "Based on your reported fasting blood sugar of 182 this morning, your doctor has instructed you to increase your insulin glargine to 17 units tonight up from 15 units yesterday."). Furthermore, all dose adjustments will be small, making them very unlikely to cause major adverse events such as hypoglycemia.

ii. Investigational drugs

None

iii. Commercially available drugs, biologics, reagents or chemicals

None

iv. Procedures

No investigational procedures will be performed.

v. Radioisotopes/radiation-producing machines

None

vi. Physical well-being

vii. Risks of participating in this study include the possibility of inaccurate self-reporting by participants leading to improper insulin dose adjustments. As stated above, our application will confirm all self-reported data prior to logging it by reading back reported values to patients and requiring verbal confirmation from the patient. Furthermore, all dose adjustments will be small (ranging from 2-4 units based on the participant's prescription). Such small dose adjustments to long-acting insulin are very unlikely to cause major adverse events such as hypoglycemia. Psychological well-being

No risk to psychological well-being. We hope that the intervention group psychologically benefits from increased engagement in their health. Furthermore, our application will provide patients with positive messages of encouragement.

viii. Economic well-being

No risk to economic well-being.

ix. Social well-being

No risk to social well-being.

x. Overall evaluation of risk

Low

b. International Research Risk Procedures

N/A

c. Procedures to Minimize Risk

As stated earlier, all prompts delivered by the application will be strictly based on the patient's physician's care plan.

d. Study Conclusion

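### Units of insulin actually taken have no documented source in either arm, although titration, time to optimal dose and adherence to a changing dose are planned outcomes

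*Protocol*

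**What the plan says.** **Outcomes planned.** Protocol Section 1.a lists among the medical outcomes "medication adherence, blood sugar control and time to optimal insulin dose". The data analysis part of Section 2.a says that insulin administration data will be used to determine "how adherent participants were to their prescribed regimen and how effectively participants were able to titrate their insulin to an effective dose".

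**Data collected, app arm.** The data collection part of Section 2.a says that at each daily check-in "the app will collect information about recently checked blood sugars and recent administration of insulin", and then sets a limit: "The only data collected from the patient will be patient-reported blood sugar data and medication administration occurrences".

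**Data collected, control arm.** Participants use a log "to record their daily blood glucose checks and insulin adherence". The columns of the log are not described in the text. A subset of app users also keeps the log for 2 of the 8 weeks.

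**Doses named anywhere.** The physician's regimen is entered through an order set or portal for both arms (Section 2.a, device setup), and the physician can change it later through the portal (Section 2.g). The app speaks a dose, for example "you should increase your dose of Lantus to 17 units". From the chart, for completers only, "the research team will obtain recent blood sugar and Hemoglobin A1c values, as well as the most recent insulin prescription".

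The SAP contains only a sample size calculation and defines no dose or adherence outcome.

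**The concern.** The regimen under study is a long-acting insulin dose that is meant to change over eight weeks. Whether a participant carried out the titration, and whether they adhered to the dose in force on a given day, depends on how many units they took and when. A record that an injection occurred does not contain that.

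The trial asks whether a voice assistant helps people carry out a titration plan at home. If dose taken is not recorded, that behaviour is not observed. What remains is the dose that was prescribed or prompted, which shows what the participant was told to do. An adherence measure built on occurrences would also miss failure to titrate, because continuing to inject an old dose every day counts as full adherence. Daily doses that are not recorded at the time cannot be recovered afterwards.

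**Working it through.** **1. The plan's own figure.** The SAP's 32 participants rest on glycemic control, 84% vs 40%, two-sided alpha 0.05, power 80%. With 1:1 allocation (assumed, as no ratio is stated) and unpooled variance:

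n per arm = (1.960 + 0.842)² × (0.84×0.16 + 0.40×0.60) / (0.84 − 0.40)² = 7.849 × 0.3744 / 0.1936 = 15.18, so 16 per arm and 32 in total.

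The figure reproduces under that formula. It uses neither dose nor adherence, so this point does not change it.

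**2. Does any documented source give units taken?**

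| Source | Arm | What it documents |
|---|---|---|
| Portal or order-set regimen (2.a, 2.g) | both | dose prescribed and titration parameters |
| App prompt (2.a, 7.a) | app | dose called for |
| Daily check-in (2.a) | app | glucose and occurrence of administration; amount not stated |
| Log (2.a) | control; a subset of the app arm for 2 of 8 weeks | glucose and adherence; columns not shown |
| Chart (2.a) | completers, both arms | latest prescription only |

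Every dose named is an intended dose. The worked example in Section 7.a fits this pattern: "Based on your reported fasting blood sugar of 182 this morning, your doctor has instructed you to increase your insulin glargine to 17 units tonight". The only item it labels as reported is the glucose value. The app speaks both doses, and the origin of the earlier 15 units is not stated. The single chart prescription cannot date self-titration steps.

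**3. What an occurrence measure misses.** Inputs: the example rule in Section 2.a (2 units every 3 days if not at goal) and 8 weeks = 56 days. Assumptions: goal is never reached, no maximum dose applies, and an injection is taken every day.

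- Steps called for: floor(56/3) = 18.
- Rise in dose called for: 18 × 2 = 36 units.
- Gap at week 8 if a fraction f of steps is not taken: f × 36 units.

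| f (assumed) | Occurrence adherence | Gap between dose called for and dose taken |
|---|---|---|
| 25% | 100% | 9 units |
| 50% | 100% | 18 units |
| 100% | 100% | 36 units |

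The fractions are illustrative; the documents give no rate of missed steps. The 36 units are the ceiling for this example rule only. Section 7.a describes adjustments of 2 to 4 units, and Section 4.a lets the provider cap the dose and limit the increases, and describes a hypoglycemia protocol that can lower the dose or switch titration off.

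**The case against.** The case on the other side has real weight.

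- **The sentence may not be a field list.** It sits in a paragraph on the manual, audio and privacy, and the same section describes collecting information about recent insulin administration, which could include the amount. The authors also plan to assess titration from administration data, which suggests that they expected a dose in them. This stands as far as it goes: the plan does not expressly exclude units. But the sentence is worded as a limit, and nothing else in the text supplies the amount.
- **The deciding attachments are not available.** The log forms, the setup instructions and the screenshots may show a units field. This stands. It rules out saying that the control arm has no dose record, or that titration cannot be measured. What can be said is that no source is documented.
- **The dose called for can be reconstructed.** The starting regimen is recorded for both arms, so with logged glucose the dose called for can in principle be derived in each. This stands, and it is useful, but the result is still not the dose taken.
- **Time to optimal dose could be defined by glucose.** It might mean time to goal fasting glucose, which both arms record. That is possible, since the endpoint is undefined. It would then be a glucose outcome, and adherence and titration would still need a dose.
- **The 36 units are an extreme case.** Agreed; the figure shows what the measure can miss and does not estimate what will happen in this trial.

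A reader might also infer that the prompted dose will stand in for the dose taken in the app arm and tilt the comparison towards the app. The documents do not say that the prompt will be used in this way. The direction of any bias would also depend on control log columns that cannot be seen.

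**Conclusion.** The point holds as a mismatch between planned outcomes and documented data. Followed as written, the app records that insulin was taken but not how much. No text in the protocol or SAP documents units taken in either arm, so uptake of titration is not observed and adherence to a changing dose can be scored as complete when no change was made.

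The size is bounded only by illustration: up to 36 units over 56 days under the example rule, with goal never reached and no cap. The conclusion rests on reading an occurrence as an event without an amount, and on the text alone. If the attachments already capture units in both arms, what remains is to correct the limiting sentence and define the outcomes on those units.

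The documents do not support three stronger readings: that these outcomes are impossible to measure, that the arm comparison is biased in a known direction, or that the sample size is affected.

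**What to change.** 1. Record dated units of long-acting insulin taken, in the same way in both arms: one item in the daily check-in with the existing read-back confirmation, and a units column on both log forms if they do not already have one.
2. Amend the limiting sentence in Section 2.a so that it includes units taken.
3. Define the titration and adherence outcomes in the SAP on units taken. Keep the dose called for, derived from the portal regimen and logged glucose, as a separate variable in both arms. State in advance how agreement between the two is scored, and report occurrence adherence as supporting. State whether time to optimal dose is defined by dose or by glucose.
4. If units taken will not be collected, label these outcomes as prescribed or prompted dose and make no claim about titration uptake.

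Cost: slightly longer check-ins, a small app change with retesting, possibly one log column, and a wording amendment. No extra staff, visits or procedures are needed. It should be settled before participants start logging.
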